This pilot seeks to utilize two principle-driven interventions, message framing and reinforcement learning, to motivate adherence to evidence-based medications for adults with type 2 diabetes. To accomplish this aim, this project consists of two phases. **This present protocol focuses only on the second phase, which is a small pragmatic trial.**

This phase has the following aims:

- (A) *To determine whether a novel reinforcement-learning text messaging program improves adherence to medications and clinical outcomes.* We will conduct a small pragmatic trial to determine the feasibility and efficacy of using reinforcement learning on patient adherence to diabetes medications.
- (B) *To classify patient responsiveness to reinforcement learning.* We will cluster intervention patients by their response to different types of messages (e.g., negative or positive framing) and evaluate the ability to predict these cluster phenotypes using information prior to randomization. This approach will optimize the design of future interventions by eliminating the need for electronic pill monitoring to determine clusters.

Subject Selection

Phase 2: Pragmatic Trial

- We will enroll and randomize 60 eligible male and female patients (30 each to intervention and usual care arms) receiving their care at a BWH-affiliated diabetes practice who are between 18-84 years of age with type 2 diabetes mellitus (T2DM) and are prescribed between 1-3 daily oral medications for this disease. Patients must have a smartphone with a

Detailed Protocol – Reinforcement Learning in Diabetes Mellitus Trial

PI: [name]

Version 5. April 1 2021

data plan or WiFi at home, an HbA1c level $\geq 7.5\%$, basic working knowledge of English, no active enrollment in another diabetes trial within Mass General Brigham, and ability to set up the platform and adhere to study procedures. To be included, patients must also either not currently use a pillbox or be willing to use electronic pill bottles (EDMs) for their diabetes medications for the duration of the study. This criterion is primarily because if patients were to concomitantly use pillboxes for these medications, it would undermine our ability to measure their adherence patterns.

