We will include the below text in secure emails or via Partners Patient Gateway, so that patients will have the ability to opt-out:

"The Mass General Brigham (MGB) standard is to send email securely. This requires you to initially set up and activate an account with a password. You can then use the password to access secure emails sent to you from MGB. If you prefer, we can send you "unencrypted" email that is not secure and could result in the unauthorized use or disclosure of your information. If you want to receive communications by unencrypted email despite these risks, MGB will not be held responsible. Your preference to receive unencrypted email will apply to:

for research: [emails sent to you from research staff in this study. If you wish to communicate with other research staff at MGB regarding additional studies, your preference will have to be documented with each research group.]

for clinicians: [emails sent from clinicians and staff at this practice or department.]

for finance: [emails sent to you from Patient Billing Solutions and the Patient Service Center.]

Please confirm receipt of this email and indicate if your preference is to NOT receive secure emails from me at this time. If I do not hear back from you, then all future emails will be sent either via patient gateway or via secure messaging as is MGB policy."

Detailed Protocol – Reinforcement Learning in Diabetes Mellitus Trial

PI: [name]

Version 5. April 1 2021

Patients who prefer to correspond via email and to complete surveys electronically, will have the option to do so securely via the above channels for email and via REDCap, with all links sent securely as well.

Study Procedures

Participants have two study-related visits. These study visits can be completed virtually or in-person during clinic visits (if/when COVID-19 precautions are lifted) and both sets of procedures are described in further detail below.

Using a random number generator using stratification by baseline self-reported adherence and HbA1c control, the study research assistant will randomize 30 patients to the reinforcement learning arm and 30 patients to usual care. Other clinic staff and analysts will be blinded to arm assignment.

Virtual Study Procedures

1st Virtual Study Visit

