Before beginning follow-up, subjects in both arms will be contacted within 2 business days to review procedures, confirm the functionality of their bottles, and verify cellphone numbers for delivery of the intervention.

[figure not shown]
Trial Period

The trial period protocol for the in-person study participants is exactly the same as the protocol for the virtual study participants described above.

2nd Study Visit

At the 2nd study visit, participants will be offered a \$50 Amazon gift card, and they will be able to keep their Pillsy EDM device(s) for personal use. Participants will also be asked to complete a questionnaire about their self-reported medication use and adherence and perspectives on the intervention (if applicable) or EDM monitors.

Study Schema

Outcomes

The trial's primary outcome is medication adherence assessed in the 6 months after randomization. Medication adherence will be measured by averaging daily adherence (as described above) for each medication across each patient beginning the day after randomization until 180 days after randomization. Secondary outcomes include change in glycemic control as assessed using HbA1c, and self-reported adherence at the end of follow-up. HbA1c values will be collected from routine measurements recorded in the EHR system; we will use the value closest to each patient's 6-month end of follow-up, up to 1 month after

Detailed Protocol – Reinforcement Learning in Diabetes Mellitus Trial

PI: [name]

Version 5. April 1 2021

randomization. In routine care, HbA1cs are measured approximately every 3-6 months, so we expect only modest missingness, as we have observed also in prior work. Self-reported adherence will be assessed as the proportion of patients who are adherent according to a validated 3-item self-report measure and prior literature from the follow-up questionnaire.³¹ We will also descriptively measure implementation outcomes informed by the RE-AIM framework⁵³, including representativeness of patients in the study, text messaging opt-out rates, any feedback from patients, and rates of pill bottle disconnectedness, which will inform considerations for how to scale the intervention to other settings.

Statistical Analysis

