We will report means and frequencies of pre-randomization variables separately by intervention and control arm, comparing these values using absolute standardized differences. The outcomes will be evaluated using intention-to-treat principles among all randomized participants. In the primary analysis, we will evaluate adherence and glycemic control using generalized estimating equations with an identity link function and normally distributed errors. We will also adjust for the block randomized design. We do not expect any missing data for the primary outcome, but may have up to 25% missingness for the glycemic control outcome. If >10% of participants have missing HbA1c data, we will repeat our analyses using multiple imputation. A similar approach will be taken for self-reported adherence, except using a log link function and Poisson distributed errors to generate relative risks of the proportion of adherent patients in the intervention versus control arms. In secondary analyses, we will control for any differences in baseline variables between the arms despite randomization.

As a sensitivity analysis, we will censor patients in the analysis when they have stopped using the electronic pill bottle for >30 days. We will also evaluate the change in HbA1c from baseline until the end of follow-up and differences in self-reported adherence separately for the 3 items that make up the self-reported scale we are using. For glycemic control (HbA1c) and self-reported adherence, we will also conduct complete case analyses. Similarly, subgroup analyses will include stratification by age, sex, race/ethnicity, baseline HbA1c, baseline self-reported adherence, and number of study medications.

Our study should be sufficiently powered to detect clinically meaningful differences in the primary outcome. With 60 subjects, we estimated that we would have the power to detect a 10% difference in average adherence over the 6-month follow-up period between the 2 arms, assuming a standard deviation (SD)=12.5%, power=0.8, and alpha=0.05. With this sample size, we would also be able to detect an HbA1c difference of 1.0% between arms (assuming SD=1.3) and 50% relative difference in self-reported adherence.

Risk and Discomforts

We believe that the risks to participation for subjects are no more than minimal. We do not anticipate the occurrence of any incremental adverse events as a result of patients receiving

Detailed Protocol – Reinforcement Learning in Diabetes Mellitus Trial

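### The main HbA1c analysis should include continuous baseline HbA1c, which every patient already has; without it, some power is lost and the level and change results can differ

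*Combined protocol and SAP*

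**What the plan says.** - **Main model (Statistical Analysis).** "In the primary analysis, we will evaluate adherence and glycemic control using generalized estimating equations with an identity link function and normally distributed errors". The next sentence adds adjustment for the blocked randomization, without listing terms. No continuous baseline HbA1c covariate is named.
- **Randomization (Study Procedures).** "Using a random number generator using stratification by baseline self-reported adherence and HbA1c control". HbA1c control is therefore a category; no cut-point is given.
- **Eligibility (Subject Selection).** Entry requires "data plan or WiFi at home, an HbA1c level" of at least 7.5%, so each patient has a value before randomization.
- **Outcome (Outcomes).** "Secondary outcomes include change in glycemic control as assessed using HbA1c". For the follow-up measurement, "we will use the value closest to each patient's 6-month end of follow-up". The source is routine care: "HbA1c values will be collected from routine measurements recorded in the EHR system". The text does not say which routine value is the baseline.
- **Change analysis (Statistical Analysis, sensitivity paragraph).** "We will also evaluate the change in HbA1c from baseline until the end of follow-up".
- **Missing data.** Up to 25% missing HbA1c is allowed for. "If >10% of participants have missing HbA1c data, we will repeat our analyses using multiple imputation".
- **Other baseline adjustment.** Covariates that differ between the arms are adjusted for in secondary analyses only, with no cut-off or list. Baseline HbA1c is otherwise named only as a subgroup factor.
- **Power.** 60 patients are said to suffice for a 1.0-point HbA1c difference with SD 1.3. Whether 1.3 is the SD of level or of change is not stated.

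**The concern.** Baseline HbA1c is likely to be among the strongest predictors of follow-up HbA1c, and a stratum indicator keeps only part of that information. Leaving out the continuous value has two consequences.

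First, power is given away on an outcome that may lose a quarter of its data.

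Second, the plan has two HbA1c analyses, apparently level as the main one and change as an additional one. With strata adjustment only, their estimates differ by whatever baseline imbalance remains within strata. The label in Outcomes points to change and the model points to level, so a reader cannot be sure which estimate is the main one.

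A smaller point concerns the secondary adjusted analyses: with no cut-off and no list, chance imbalance chooses the covariates.

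**Working it through.** **Inputs from the documents.** 30 patients per arm; difference 1.0; SD 1.3; alpha 0.05 (two-sided assumed); up to 25% missing HbA1c, which leaves 45 patients, taken as 23 and 22.

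**Assumptions, not in the documents.** Baseline to follow-up correlation ρ = 0.3, 0.5 or 0.7; equal SDs at the two times; bivariate normal values; HbA1c stratum a median split. The plan is credited with adjusting for that stratum.

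**The plan's own figure.** With no covariate, 1.0 and SD 1.3 need 27 per arm (54 in total). With 30 per arm the power is 0.834 (t) or 0.846 (normal). The statement that 60 patients suffice therefore holds. With 45 patients the power is 0.713 (t).

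**Residual SDs.** A median split of a normal variable correlates √(2/π) with it. With s the SD of level:
- follow-up level, strata only: s√(1 − 2ρ²/π)
- follow-up level, continuous baseline: s√(1 − ρ²)
- change, strata only: s√[(1 − ρ)²(1 − 2/π) + 1 − ρ²]

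For s = 1.3 and ρ = 0.5 these are 1.192, 1.126 and 1.192.

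**Power for 1.0 (noncentral t), ρ = 0.3 / 0.5 / 0.7, with 1.3 as the SD of level**

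| Model | 60 patients | 45 patients |
|---|---|---|
| Level, strata only | 0.855 / 0.892 / 0.942 | 0.738 / 0.785 / 0.860 |
| Change, strata only | 0.802 / 0.892 / 0.978 | 0.676 / 0.785 / 0.928 |
| Continuous baseline added | 0.867 / 0.923 / 0.984 | 0.753 / 0.829 / 0.942 |

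Taking off degrees of freedom for the covariates changes power by at most 0.002.

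**If 1.3 is the SD of change.** Then s = 1.3/√(2(1 − ρ)) = 1.099 / 1.300 / 1.678.

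| Model | 60 patients | 45 patients |
|---|---|---|
| Level, strata only | 0.946 / 0.892 / 0.781 | 0.867 / 0.785 / 0.653 |
| Continuous baseline added | 0.953 / 0.923 / 0.888 | 0.878 / 0.829 / 0.781 |

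**Truncated baseline.** Eligibility cuts baseline off at 7.5%, so the level model was also simulated: baseline normal, left-truncated 0.5 SD below its mean and rescaled to SD 1.3; four strata; permuted pairs; 8,000 trials per setting. Strata only versus continuous baseline:
- 60 patients: 0.851 / 0.892 / 0.940 versus 0.855 / 0.920 / 0.980
- 45 patients: 0.729 / 0.774 / 0.852 versus 0.735 / 0.808 / 0.932
- 25% missing at random, multiple imputation (20 imputations, baseline HbA1c in the imputation model, 6,000 trials): 0.712 / 0.765 / 0.863 versus 0.719 / 0.791 / 0.923

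The closed-form figures have been checked independently; the simulated ones have not been repeated.

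**Gap between the level and change estimates.** In the same patients, the level estimate minus the change estimate equals the strata-adjusted arm difference in baseline HbA1c. Its SD is s_b·√(1 − 2/π)·√(1/n₁ + 1/n₂), with s_b the baseline SD. It does not depend on ρ once s_b is fixed.

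| s_b | Arms | SD of gap | P(gap beyond ±0.2) |
|---|---|---|---|
| 1.3 | 30/30 | 0.202 | 0.32 |
| 1.3 | 23/22 | 0.234 | 0.39 |
| 1.0 | 30/30 | 0.156 | 0.20 |
| 1.099 | 30/30 | 0.171 | 0.24 |
| 1.678 | 30/30 | 0.261 | 0.44 |

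The 0.2 mark is an assumed yardstick. With the truncated baseline the simulated gap SD was 0.20 to 0.21 (60 patients) and 0.23 to 0.24 (45). With a strongly skewed baseline and 60 patients it was 0.24 to 0.25 for a median cut and 0.20 for a 75th-percentile cut. With continuous baseline in the model the gap is exactly zero, because subtracting a covariate already in a linear model shifts only that covariate's own coefficient.

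**Imbalance-driven covariates (minor).** The standardized difference of a null, continuous, unstratified covariate has SE √(2/30) = 0.258. It exceeds 0.1 with probability 0.70 and 0.2 with probability 0.44 (cut-offs assumed).

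**The case against.** The strongest case is that little is at stake. This is a 60-patient pilot and a secondary outcome. If 1.3 is the SD of level, power with complete data is at least 0.85 under the strata-only level model, above the planned 0.80. Randomization makes both the level and the change analysis unbiased for the same effect. A gap SD of 0.20 should be set against a standard error of about 0.28 to 0.33 for the level estimate and a target of 1.0. Main and sensitivity results commonly differ somewhat. The correlation is unknown, and with an undated routine baseline value it could be low, leaving a gain of about one point. All of this stands and limits the weight of the point.

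A second argument is that the plan already handles imbalance, because differing baseline variables are adjusted for in secondary analyses. A baseline difference of 0.2 is 0.2/1.3 = 0.15 SD, which would trigger adjustment under a cut-off of 0.1. But the plan states no cut-off, and that analysis leaves the main estimate as it was.

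Third, if the main outcome is change, the gain follows a different pattern. With 60 patients it is 6.5, 3.1 and 0.6 percentage points at ρ = 0.3, 0.5 and 0.7. That is correct, but the continuous term still gains power at each value, so this reading does not remove the concern.

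**Conclusion.** The concern holds. The main HbA1c model names no continuous baseline term, although the value exists for every patient and the planned change analysis needs it anyway.

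With 1.3 as the SD of level and ρ between 0.3 and 0.7, the gain over strata-only adjustment of level is about 0 to 4 percentage points of power with 60 patients and 1 to 8 with 25% missing. At ρ = 0.5 with 45 complete patients it takes power from 0.785 to 0.829. If 1.3 is the SD of change, the gain at ρ = 0.7 reaches 10.7 points with 60 patients and 12.8 with 45. These sizes rest on the assumed correlation, the median split and equal SDs.

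The gap between the two planned analyses, with an SD of about 0.16 to 0.26 HbA1c points at 30 per arm across the baseline SDs tabulated, would disappear.

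The issue is precision and prespecification, not bias. The stated power figure is not wrong because of it, and no gain is claimed for the primary adherence outcome. The change is worth making because it needs no new data. The covariate-selection and wording items are minor.

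**What to change.** 1. Add baseline HbA1c as a continuous covariate to the main HbA1c model, alongside the two stratification factors. Define it as the last value before randomization, and include it in the imputation model. State that the arm effect is then the same for follow-up level and for change.
2. Make the outcome label in Outcomes match that model.
3. Minor: in the secondary adjusted analyses, replace adjustment for observed differences with a short covariate list fixed in advance on prognostic grounds.
4. Wording only: name baseline self-reported adherence and HbA1c control as the design terms, and say whether 1.3 is the SD of level or of change.

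The cost is a few sentences in the analysis section. Baseline HbA1c and both stratification factors are already obtained before randomization.

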Subjects will provide written informed consent for all study procedures, including the use of text messages, and be enrolled at Brigham and Women's Hospital. The study staff will conduct the consent discussion via video and obtain paperless consent or e-consent from the participant through the MGB approved REDCap e-consent platform. After this visit, they will be mailed an electronic pill bottle manufactured by Pillsy along with written instructions for setup (see Attachments), which participants will be asked to use for the duration of the study. Based on data from prior trials, poorly-controlled patients with type 2 diabetes take an average of two oral glucose-lowering medications, and we expect to distribute approximately two EDMs per patient but no more than three.

At the baseline visit, we will also collect some basic information from subjects to administratively manage the study: name, address, email address, telephone number and the best times and days to contact, in addition to sociodemographic information (see demographics baseline questionnaire). For the patient to complete the surveys in the REDCap database, we will provide them with a secure link to the online database so they can complete the surveys at their convenience. The survey invites will be sent via secure email or SMS using the Twilio platform, a third-party web service integrated into REDCap, which will provide the participant with the survey URL, depending on patient preference. We will review contact information with subjects at each study visit to make sure that we have the most accurate information. Contact information will be stored in the password-protected REDCap database.

Additional information on demographics, diagnoses, medications, comorbidities, laboratory tests and disease activity will be abstracted from participants' medical records. Data will be collected through chart review as well as RPDR and entered into our REDCap database.

Before beginning follow-up, subjects in both arms will be contacted within 2 business days to review procedures, confirm the functionality of their bottles, and verify cellphone numbers for delivery of the intervention.

Detailed Protocol – Reinforcement Learning in Diabetes Mellitus Trial

PI: [name]

Version 5. April 1 2021

Optional Check-in

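### The secondary adjusted analyses choose covariates by chance imbalance between arms; a short fixed prognostic set would be a better and nearly free choice

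*Combined protocol and SAP*

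**What the plan says.** In the combined protocol and SAP, Statistical Analysis, pre-randomization variables are summarized by arm, "comparing these values using absolute standardized differences". The primary analysis adjusts for the randomization design. The covariate rule for the adjusted analyses then reads: "In secondary analyses, we will control for any differences in baseline variables between the arms despite randomization". No cut-off, candidate list or fixed set is given there or elsewhere.

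The pool of possible variables is open. Both first-visit descriptions (virtual and in-person) say: "Additional information on demographics, diagnoses, medications, comorbidities, laboratory tests and disease activity will be abstracted". Statistical Analysis also names six subgroup variables. Two of them, baseline HbA1c and baseline self-reported adherence, correspond to the stratification factors given under Study Procedures.

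**The concern.** Under randomization, an observed baseline difference carries no information about whether the variable predicts adherence or HbA1c. Selecting on it has two costs. Variables with no prognostic value enter the model and use up precision. Prognostic variables that happen to be balanced stay out, although adjusting for them would have reduced residual variance. The stratification factors should be roughly balanced by design, so this rule is unlikely to select them, even though they are plausible predictors (an assumption). The design adjustment may carry them, but the plan does not name them there.

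The model also stays undefined until the arms have been compared. At stake are the precision and the prespecification of the secondary adjusted results in a 60-patient trial.

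**Working it through.** **Inputs from the document.** Allocation is "30 each to intervention and usual care arms" (Subject Selection). The design effect and its assumptions are in Statistical Analysis: "With 60 subjects, we estimated that we would have the power to detect a 10% difference in average adherence", "assuming a standard deviation (SD)=12.5%, power=0.8, and alpha=0.05". On dropout: "We do not expect any missing data for the primary outcome".

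**Inputs assumed.** The plan does not give the number of candidate variables (6, 10, 15 or 20 tried), their joint R² with the outcome (0 to 0.5 tried), the imbalance cut-off (mainly 0.1, also 0.2) or the sidedness of the test (two-sided taken).

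**1. The plan's own power figure.**
- Required n per arm = 2 × 12.5² × (1.96 + 0.842)² / 10² = 24.5, so 25 per arm or 50 in total (52 with a t-based calculation).
- At 30 per arm the SE is 12.5 × √(2/30) = 3.23 points. Power is Φ(10/3.23 − 1.96) = 0.87, or 0.86 by the noncentral t.
- The stated 0.80 is therefore not reproduced, but the difference is on the safe side. The detectable difference at 0.80 power is 2.80 × 3.23 = 9.0 points. The unadjusted benchmark below is 0.86.

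**2. How often chance alone selects a variable.** For a continuous variable, the SD of a standardized difference is √(2/30) = 0.258, and P(|d| > c) = 2 × [1 − Φ(c/0.258)].
- c = 0.1: 0.70
- c = 0.2: 0.44
- c = 0.25: 0.33

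Binary variables with prevalence 0.1 to 0.5 give 67–78% at 0.1 and 45–52% at 0.2. At a cut-off of 0.1 the expected number entered is 0.70 × 6 = 4.2, 0.70 × 10 = 7 or 0.70 × 20 = 14. Of four truly prognostic variables, 4 × 0.30 = 1.2 are left out on average.

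**3. Effect on power.** Simulation used 30 per arm, a 10-point effect, SD 12.5, independent normal covariates, a linear model and 3,000–4,000 trials per setting. Four variables carried a joint R² of 0.25, and the cut-off was 0.1.

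| Candidates | Entered (mean) | Imbalance rule | Correct fixed set | Unadjusted |
|---|---|---|---|---|
| 6 | 4.2 | 0.91 | 0.93 | 0.86 |
| 10 | 7 | 0.88 | 0.93 | 0.86 |
| 20 | 14 | 0.79 | 0.92 | 0.86 |

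A repeat run with another seed gave 0.90, 0.87 and 0.80 for the rule, so these figures are good to about 0.01–0.02.

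**4. Against no adjustment.** In the same design, the SD of the treatment estimate (rule against unadjusted) was:
- 6 candidates: 3.00 against 3.23
- 10 candidates: 3.03 against 3.22
- 15 candidates: 3.20 against 3.23
- 20 candidates: 3.39 against 3.19

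The rule gains with few candidates, roughly breaks even at 15 and loses at 20. If the candidates predict nothing (R² = 0), it loses throughout: power is 0.81, 0.80 and 0.72 with 6, 10 and 20 candidates, against about 0.86.

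**5. Against a fixed prognostic set.** The rule had lower power in every setting tried with R² of 0.1 or more. For example, with R² 0.3 on two variables and 10 candidates, the SD was 2.97 against 2.73 and power 0.89 against 0.95.

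**6. Validity.** Bias was negligible. Type I error with model-based standard errors was 0.02–0.06. The plan uses GEE and does not state the type of standard error. With an uncorrected sandwich estimator, 20 candidates and a cut-off of 0.1, type I error was about 0.10.

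**The case against.** The strongest reply is that little depends on this sentence. The primary analysis adjusts only for the design, so no primary estimate, p-value or sample size is affected. The rule looks at baseline data and arm, not outcomes, so it does not search for a favourable effect, and Study Procedures states that analysts are blinded to arm assignment. All of this stands, and it limits the point to an improvement of a secondary analysis.

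The comparator is also generous. Power of 0.93 assumes that the team names exactly the prognostic variables. If two are named and only one is prognostic, power is about 0.87–0.88, close to no adjustment. If neither predicts anything, the fixed set costs a little (SD 3.27 against 3.21). This also stands: the gain depends on how well the set is chosen.

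A reader might infer three stronger things.
- *The rule is generally worse than leaving covariates out.* The documents do not support this. They give no candidate count, and with 6 to 10 candidates and R² of 0.25 the rule does better than no adjustment.
- *Most variables will be pulled in.* That needs a cut-off near 0.1 or a literal reading of the sentence. At 0.2 the figure for continuous variables is 44%, and the plan states no cut-off.
- *The adjusted result would be biased or its test invalid.* The simulations showed negligible bias and, with model-based standard errors, no material inflation. The 0.10 figure needs a sandwich estimator and a candidate count that the plan does not specify.

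What the reply does not remove is that imbalance is the wrong criterion for choosing covariates, and that the plan states it as the rule.

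**Conclusion.** The point holds as a low-cost improvement to the secondary analyses. The plan selects covariates on observed imbalance, without a list or threshold, and that criterion is unrelated to prognostic value. At a cut-off of 0.1 and joint R² of 0.25, the cost against a correctly chosen fixed set is about 0.02 in power with 6 candidates (0.91 against 0.93), 0.05 with 10 (0.88 against 0.93) and 0.13 with 20 (0.79 against 0.92). Against no adjustment, a loss is shown only for many or weakly prognostic candidates.

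The chance-selection percentages follow from 30 per arm once a cut-off is assumed. The power figures also rest on assumed candidate counts and R², independent normal covariates, one record per patient and a linear model. The log-link model for self-reported adherence was not simulated. The primary analysis is unaffected.

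**What to change.** Replace the sentence in Statistical Analysis with:

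> In secondary analyses we will adjust for a short fixed set of covariates chosen for expected prognostic value and named before arm labels are released (for example continuous baseline HbA1c and baseline self-reported adherence, plus at most a few others such as age and number of study medications), whatever their observed balance. Standardized differences are descriptive only and do not select covariates.

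The cost is one sentence and no new data. There are two downsides. A chance imbalance in an unlisted variable stays unadjusted, which remains valid under randomization. A poorly chosen set gains little or loses slight precision, so the set should be short and each variable should have a stated reason.
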